### 3 INVESTIGATIONAL PLAN

#### 3.1 Overall Study Design and Plan

[figure not shown]
This is Phase II, modular, open label, multicentre, study to evaluate the preliminary efficacy and safety of RXC004 monotherapy in advanced solid tumours that have progressed following standard of care treatment.

The study initially opened with ring finger protein 43 (RNF43) loss of function (LoF) mutation-positive pancreatic ductal adenocarcinoma (PDAC) (Module 1) and biliary tract cancers (BTC) (Module 2). The purpose of Module 3 is to evaluate RXC004 1.5 mg in combination with pembrolizumab in patients with BTC. [CC1] [REDACTED] evaluable patients will be enrolled in each module.

The primary objective of the study is to assess the preliminary efficacy of RXC004 in each module in terms of progression free survival (PFS) at 6 months. Tumour assessment will be performed by Investigators every 6 weeks  $\pm$  1 week (relative to the date of initiation of study treatment) for the first 54 weeks, followed by q12w  $\pm$  1 week until radiological disease progression (as defined by Response Evaluation Criteria in Solid Tumours, version 1.1 [RECIST 1.1]). Following radiological progression, patients will be followed-up for safety and survival.

The general study design is summarized in [Figure 1](#).

Figure 1 - Overall Design

DCR, disease control rate; CCI [REDACTED] ECOG performance status, LoF, Loss of Function, ORR objective response rate; OS Overall survival; PFS progression free survival; KP Kamofsky performance status; RNF43 Ring finger 43; RXC004 Porcupine inhibitor.

The analyses will be conducted independently for each module. The module data will be locked before their analyses. All the populations and endpoints described hereafter must be considered independently for each module.

### 3.2 Endpoints and Associated Variables

#### 3.2.1 Efficacy Variables

The following variables will be used to evaluate efficacy endpoints:

- In accordance with RECIST 1.1 guidelines (see Section 66):
  - PFS
  - ORR based on each patient's BOR
  - DCR based on each patient's BOR
  - Percentage change at each visit and best overall percentage change in the sum of target lesions
  - CCI [REDACTED]
  - CCI [REDACTED]

- Overall Survival (OS)

In case the RECIST 1.1 assessment will be done across several days:

- The first day of assessment will be considered in case of progressive disease (PD) as overall response (OR).
- The last day of assessment will be considered in case of response (complete response [CR], partial response [PR] or stable disease [SD]) as OR.

### 3.2.1.1 Progression Free Survival

PFS is defined as the time from first dose of study treatment (C0D1) until the date of disease progression or death (by any cause in the absence of progression), regardless of whether the patient withdraws from the assigned study treatment or receives another anticancer treatment prior to progression.

Patients who have not progressed or died at the time of analysis will be censored at the time of the latest date of RECIST 1.1 assessment of their last evaluable scan, however if the patient progresses or dies after 2 or more missed scheduled scanning visits (Progression/Death date - Last available scan date $\geq$ 12 +1 weeks), the patient will be censored at the time of their last evaluable scan prior to the missing scan visits. If the patient has no evaluable visits or does not have baseline data, they will be censored at 0 days. However, if the patient dies within 2 scan visits of first dose (within 12 + 1 weeks from first dose date without a post baseline scan) then its death date will be treated as their progression date. Progression free survival rate at 6 months is the primary endpoint. PFS time is defined as:

$$\text{PFS (days)} = \text{Date of documented PD, Death or last RECIST 1.1 assessment} - \text{first dose of study treatment (C0D1)} + 1$$

Progression free survival rate at 6 months will be defined as the proportion of patients alive and progression free at 6 months.

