8.1.1 Tumour Assessments

Tumour assessments use images from CT or MRI, collected during screening/baseline and at regular (follow-up) intervals during the study. The same imaging method should be used throughout the study. It is important to follow the tumour assessment schedule as per the SoA. Tumour assessments will continue until RECIST1.1-defined radiological progression. Scan timing should follow calendar days and should not be adjusted for delays in cycle starts.

Sites will be required to store electronic copies of all scans until study closure, and the Sponsor may arrange for possible centralised storage of all anonymised imaging data. Centralised storage of imaging data would be possible to support an independent centralised review of disease assessments.

In addition, if available, the last 2 imaging scans taken prior to the screening scan for this study and/or their reports should be kept for possible central/sponsor review.

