8.3.7.1 Management of Biliary Tract Obstruction

In the event of the development of obstructive jaundice due to biliary tract obstruction, appropriate measures should be undertaken to diagnose (e.g. by ultrasound and/or CT scan) and relieve the obstruction (e.g. by ERCP/PTC +/- stent insertion/drainage). Treatment will be delayed until the LFTs have improved to pre-obstruction levels.

Biliary tract obstruction by itself shall not constitute evidence of disease progression. CT or MRI/MRCP imaging will be performed at the planned time points; however, if there is radiological evidence of objective disease progression during the investigation of obstructive jaundice, treatment with RXC004 shall be discontinued.

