9.4.2.2 Secondary Endpoint(s)

Objective response rate is defined as the proportion of patients with a best overall response of CR or PR, based on local investigator assessment, as defined in RECIST 1.1. Confirmation of response is required for declaring PR or CR as the BOR. A confirmed response is defined as a CR or PR followed by a CR or PR a least 4 weeks later. The ORR will be summarised with accompanying 90% confidence interval calculated using the Clopper Pearson method. This will be calculated on the full analysis set and the evaluable analysis set. In the summary tables the incidence of unconfirmed responses will be presented as well as the patients with confirmed responses.

Disease control rate (DCR) is defined as the proportion of patients with a best overall response of either CR, PR or stable disease (SD) for at least 6 weeks (corresponding to SD for at least 1 scheduled scan post baseline). A time window of 1 week around the visit will be applied. The DCR and associated 90% confidence interval, calculated using the Clopper Pearson method will be presented. This will be calculated on the full analysis set and the evaluable analysis set.

Progression free survival is defined as the time from first dose of study treatment until the date of disease progression or death (by any cause in the absence of progression), regardless whether the patient withdraws from the assigned study treatment or receives another anticancer prior to progression. Patients who have not progressed or died at the time of analysis will be censored at the time of the latest date of RECIST v1.1 assessment of their last evaluable scan; however, if the patient progresses or dies after 2 or more missed scheduled scanning visits, the patient will be censored at the time of their last evaluable scan prior to the missing scan visits. If the patient has no evaluable visits or does not have baseline data they will be censored at 0 days unless they die due to progression within 2 scan visits of baseline. Progression free survival will be listed by patient and will be presented graphically using Kaplan-Meier plots. Median PFS, together with 3 month, 6 month and 12 months PFS rates will be estimated. The estimate for PFS rate at 6 months is the primary endpoint as detailed in Section 9.4.2.1.

[figure not shown]

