#### **4.2.4 End of Study (EoS)**

A patient is considered to have completed the study if he/she has completed all phases of the study (including the last visit and the last scheduled assessment shown in the SoA) or withdraws consent whichever occurs first.

The EoS is defined as the date of the last visit of the last participant in the study or the last scheduled assessment shown in the SoA for the last participant in the study before the data cut off (DCO). The study data is planned to be analysed and reported based on all patient data at the primary completion data cut-off date (approximately 24 weeks after cycle 1 day 1 for the last patient in), or at the End of Study, whichever comes first.

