#### 4.11.2.1 Progression Free Survival

PFS is defined in Section 3.2.1.1.

Kaplan-Meier analyses will be conducted for each module. Survival plots will be produced to present Kaplan-Meier estimated curves. In addition, the following parameters estimated from the Kaplan-Meier curves will be provided for each group:

- Median PFS and corresponding 95% CIs
- PFS rate at 3, 6 and 12 months and corresponding 90% CIs and 95% CI (one month = 30.4375 days).

PFS will be listed for all patients in the FAS.

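### The SAP's fixed 13-week censoring limit for PFS does not match its own two-missed-scans rule on a schedule that moves from 6-weekly to 12-weekly scans

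*SAP*

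**What the plan says.** Protocol 9.4.2.2 gives the rule in words, with no week limit: "if the patient progresses or dies after 2 or more missed scheduled scanning visits, the patient will be censored" at the last evaluable scan before the gap. SAP 3.2.1.1 repeats it and adds a number: "if the patient progresses or dies after 2 or more missed scheduled scanning visits (Progression/Death date - Last available scan date" must be at least 12 + 1 weeks. The number does not change during follow-up.

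The SAP then adds an early-death rule. A death "within 12 + 1 weeks from first dose date without a post baseline scan" counts as an event, and a patient with no evaluable visit is otherwise censored at day 0.

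SAP 3.1 sets tumour assessments every 6 weeks ±1 week, "relative to the date of initiation of study treatment) for the first 54 weeks, followed by q12w" with the same window. Protocol 8.1.1 fixes the planned dates: "Scan timing should follow calendar days and should not be adjusted for delays in cycle starts".

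SAP 4.11.2.1 reports the "PFS rate at 3, 6 and 12 months and corresponding 90% CIs and 95% CI (one month = 30.4375 days"). The 6-month rate is the primary endpoint of Modules 1 and 2; in Module 3, PFS is secondary.

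**The concern.** The SAP sentence holds two rules, one in words and one in weeks. They agree when 6-weekly scans fall on their planned days. They disagree when the ±1 week windows are used, and again once scans become 12-weekly. A programmer following the number will censor some documented progressions that the words, and the protocol, count as events.

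That matters because the rule feeds the primary endpoint of two modules. A patient can be censored only because an earlier scan was early, or the scan showing progression was late, with both inside the allowed window. The starting point for a patient without a post-baseline scan is also incomplete: first dose is named for deaths but not for progressions.

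**Working it through.** **Inputs.** The limit is from SAP 3.2.1.1, the schedule and windows from SAP 3.1 and Protocol 4.1, and the month of 30.4375 days from SAP 4.11.2.1. Days below count from first dose as day 0; the SAP's PFS time adds 1.

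**1. The plan's figure.** 2 × 6 weeks + 1 week = 13 weeks = 91 days. On planned days, one missed 6-weekly scan gives a gap of 84 days, below 91, so words and number agree.

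**2. Gaps with windows.** Let D be the planned distance between the last scan and the scan showing progression (PD), and a and b their deviations in whole days, −7 to +7. The gap is G = D + b − a, over 15 × 15 = 225 pairs. The SAP number censors if G ≥ 91. The words censor none of these rows.

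| Case | Last scan (week) | Missed | D (days) | G (days) | G (weeks) | Censored by the number |
|---|---|---|---|---|---|---|
| (a) | 6–42 | 1 | 84 | 70–98 | 10–14 | 36/225 |
| (b) | 48, PD at 66 | 1 | 126 | 112–140 | 16–20 | 225/225 |
| (c) | 54 or later | 0 | 84 | 70–98 | 10–14 | 36/225 |
| (c) | 54 or later | 1 | 168 | 154–182 | 22–26 | 225/225 |

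The 36 pairs need b − a ≥ 7: 8+7+6+5+4+3+2+1 = 36. With deviations of at most 3 days, b − a is at most 6, so 0 of 49.

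Examples: (a) scan on day 84, week 18 missed, PD on day 175 (the last day of the week-24 window) gives 91 days. (c) Scan on day 378, PD on day 469 (the last day of the week-66 window), nothing missed, also gives 91 days.

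**3. Which rates can move.** The landmarks are 3 × 30.4375 = 91.3, 6 × 30.4375 = 182.6 and 12 × 30.4375 = 365.25 days.
- (a) can move all three. In its example PFS is 176 days, an event before the 6-month landmark that becomes censoring at week 12.
- (b) censors at days 329–343 a patient whose PD is found after day 365. It can move only the 12-month rate.
- (c) starts at day 378 − 7 = 371 at the earliest, so it changes only the tail.

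**4. Start of follow-up.** With first dose as the starting point, an event at exactly 91 days is censored by the ≥ limit, yet a death on that day is an event under the early-death rule. For PD at week 12 with week 6 missed, G = 84 + b reaches 91 on 1 of 15 days. If the baseline scan were the starting point (allowed up to 6 weeks before first dose), PD at an in-window week-6 scan could lie 49 + 42 = 91 days away with nothing missed.

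**5. Size.** Assumptions, not in the documents except for the medians: exponential PFS with median 1.5–4 months (range in Protocol 10.1 and 11.5.1), 5–15% of scans missed at random, 5–30% of events being deaths, uniform drift of 0, ±3 or ±7 days, first dose as starting point, full follow-up. Both rules were applied to the same 200,000 simulated patients in each of 81 scenarios. Difference in Kaplan-Meier rate, SAP number minus visit count, in points:

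| Drift | 3 months | 6 months | 12 months |
|---|---|---|---|
| up to 3 days | 0.0 | 0.0 | −0.09 to 0.0 |
| ±7 days | −1.0 to −0.1 | 0.0 to +0.5 | 0.0 to +0.5 |

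At ±7 days the 6-month shift by median is −0.01 to +0.02 (6.5 weeks), +0.10 to +0.33 (13 weeks) and +0.14 to +0.47 (17.4 weeks). Wrongly censored patients reach about 6.5% at most, but only 0–2.1% have a last scan before the 6-month landmark. The late figures are upper bounds, because the data cut-off is "approximately 24 weeks after cycle 1 day 1 for the last patient in), or at the End of Study, whichever comes first".

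**6. Check of the replacement rule.** Take every in-window pair with the last scan at weeks 0–54 and PD at the next, second or third scheduled scan: 3 × 15 + 9 × 3 × 225 = 6,120 pairs. The SAP number departs from the words in 1 + 7 × 36 + 225 + (36 + 225) = 739. The visit-number rule under the fix departs in none.

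**The case against.** The strongest reply is that 12 + 1 weeks is a recognisable working definition, two intervals plus one window, and that its effect on the primary endpoint is slight. The top of the 6-month range needs 15% missed scans, drift spread evenly over ±7 days and a 4-month median together; the documents support neither of the first two. Decisions also rest on the totality of the data (SAP 4.15). This stands, and it limits the severity.

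A reader might infer from the rows where every pair is censored, or from 739 of 6,120, that much of the primary result is affected. The documents do not support that. Of the 739 pairs, 225 + 261 = 486 come from last scans at weeks 48 and 54, which cannot reach 6 months, and the pairs are calendar combinations, not probabilities. Likewise, the −1.0 at 3 months depends partly on censoring PD on day 91 at day 0; treating that day as inside the limit gives about −0.64.

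Neither document says when a visit becomes missed, so closing it at planned date plus 7 days is a convention, and the zero in step 6 partly follows from it. For deaths the choice is a definition to be stated, not an error to be proved.

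What the reply does not remove is the contradiction. A patient with no missed scan, or one, has not missed two. One such patient can also count in a small arm: assuming a 13-week median and other progressions found on planned days, recoding the day-84/day-175 patient raises the 6-month rate by about 2.7 points with 20 patients and 1.3 with 40. These arm sizes are illustrative, and the figures apply only if such a patient occurs.

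**Conclusion.** The point holds: the 13-week number contradicts the SAP's own words and Protocol 9.4.2.2. Of the three cases only (a) can affect the primary 6-month rate of Modules 1 and 2. The expected shift is 0.0 to about +0.5 points under the assumptions in step 5, and zero if scans keep within 3 days of plan. Case (b) can reach at most the 12-month rate, and case (c) only the tail. The unstated starting point for PD and the double treatment of day 91 are smaller gaps in the same paragraph.

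A reader might infer that the rule could reverse a go/no-go decision or inflate the stated error rates. That cannot be shown, because the sample sizes, p0, p1 and stopping counts are redacted. Severity is minor to should-fix: a stated rule for a primary endpoint is wrong as written, its likely effect is small, and the correction is cheap.

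**What to change.** Replace the fixed limit with a count by scheduled visit number:

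- Assign each in-window scan to its own visit k. Censor only if PD or death is later than the planned date of visit k+2, fixed from first dose, plus 7 days. For a week-12 scan this is day 168 + 7 = 175.
- Count visits, not calendar dates. A week-12 scan done early on day 77 is still visit week 12. Taking the next two planned dates after day 77 (days 84 and 126) would give day 133 and censor a week-24 PD after one missed scan.
- For PD at scheduled scans the rule equals a gap above 14 weeks if the last scan is at week 42 or earlier, above 20 weeks at week 48, and above 26 weeks at week 54 or later. For deaths and unscheduled PD use the date rule, since the 14-week limit can be up to 14 days too lenient.
- For a scan outside every window, state that it resets the last-evaluable-scan date and that k is the latest visit whose window has closed or been met by then. Such scans can arise under Protocol 8.3.7.1, which provides for the case "if there is radiological evidence of objective disease progression during the investigation of obstructive jaundice". A scan on day 64 then has k = week 6 and a limit of day 126 + 7 = 133, and does not stand in for a missed week-12 scan.
- With no post-baseline scan, use first dose as visit 0 for both PD and death, and treat the limit day as inside. This gives day 84 + 7 = 91, the SAP's existing early-death limit.

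Keep the 6-month landmark. The cost is SAP wording and programming: no new data, visits or patients, and no change of endpoint.

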### 3.2.1.2 Best Overall Response

BOR is defined as the best OR recorded from the start of the study treatment until PD or death for each patient. In case the progression event is death, the BOR takes into account all data collected until the last evaluable RECIST assessment before death. Only OR provided by Investigators at each RECIST 1.1 visit will be considered for variables derivation and analyses (for details, see Section 6).

Confirmation of response is required for declaring PR or CR as BOR. BOR is determined once all data on OR for the patient are known. BOR will be computed as the key efficacy variable to determine ORR and DCR.

A confirmed response is defined as a CR or PR followed by a CR or PR a least 4 weeks later (see Table 1 – Determination of Best Overall Response). A requirement for SD is that it should be met at least once no less than 6 weeks after the first dose of trial treatment/baseline assessment, otherwise the best response will be considered as not evaluable (NE) according to RECIST 1.1 guidelines. As the protocol allows a window of 1 week for the scan, a scan at least 5 weeks from start of treatment will be acceptable for SD.

**Table 1 – Determination of Best Overall Response (RECIST 1.1 BOR determination in trials where confirmation of complete or partial response is required)**

Overall response first time point	Overall response subsequent time point (at least 4- weeks after)	Best Overall Response
CR	CR	CR
CR	PR	see footnote (*)
CR	SD	SD provided minimum criteria for SD duration met, otherwise, PD
CR	PD	SD provided minimum criteria for SD duration met, otherwise, PD
CR	NE	SD provided minimum criteria for SD duration met, otherwise, NE
PR	CR	PR
PR	PR	PR
PR	SD	SD
PR	PD	SD provided minimum criteria for SD duration met, otherwise, PD
PR	NE	SD provided minimum criteria for SD duration met, otherwise, NE
NE	NE	NE

CR = complete response, PR = partial response, SD = stable disease, PD = progressive disease, NE = not evaluable

(\*) If a CR is truly met at first time point, then any disease seen at a subsequent time point, even disease meeting PR criteria relative to baseline, makes the disease PD at that point (since disease must have reappeared after CR). Best response would depend on whether minimum duration for SD was met. However, sometimes 'CR' may be claimed when subsequent scans suggest small lesions were likely still present and in fact the patient had PR, not CR at the first time point. Under these circumstances, the original CR should be changed to PR and the best response is PR.

### 3.2.1.3 Objective Response Rate

ORR is defined as the proportion of patients with a BOR of CR or PR. Confirmation of response is required for declaring PR or CR as the BOR. Responses on subsequent treatments after discontinuing will not be included.

### 3.2.1.4 Disease Control Rate

DCR is defined as the proportion of patients with a BOR of either CR, PR or SD for at least 6 weeks post-baseline (corresponding to SD for 1 scheduled scans post-baseline). As the protocol allows a window of 1 week for the scan a time window of 1 week before the Week 6 visit will be applied such that any scan that is at least 5 weeks after starting treatment will be considered acceptable for the evaluation of response.

### 3.2.1.5 Percentage change in the sum of target lesions

Percentage change in sum of diameters of target lesions from baseline for patients with measurable disease, will be calculated for each RECIST assessment visit, as follows:

Percentage change in the sum of target lesions (%) =  $(\Sigma \text{ observed value after baseline} - \Sigma \text{ observed value at baseline}) * 100 / \Sigma \text{ observed value at baseline}$

The best overall percentage change in the sum of target lesions (%), representing the largest decrease (or smallest increase in the absence of a decrease) from baseline, will also be considered as an efficacy endpoint.

### 3.2.1.6 CCI

CCI  
CCI  
CCI  
CCI  
CCI  
CCI

### 3.2.1.7 CCI

CCI  
CCI  
CCI

### 3.2.1.8 Overall Survival

OS is defined as the time from the first day of study treatment (C0D1) until death due to any cause. Any patient not known to have died at the time of analysis will be censored based on the last recorded date on which the patient was known to be alive. OS time is defined as:

OS (days) = Date of death or last contact – first dose of study treatment (C0D1) + 1

### 3.2.2 Pharmacokinetic Variables

CCI [REDACTED]

### 3.2.3 Safety Variables

The following safety variables will be evaluated:

- AEs and SAEs
- Dysgeusia
- Vital signs
- 12-lead Electrocardiogram (ECG)
- ECOG or KP performance status
- Prior and concomitant medications
- Clinical laboratory evaluation
- CCI [REDACTED]

### 3.2.4 Tertiary Endpoint

CCI [REDACTED]

CCI [REDACTED]

CCI [REDACTED]

CCI [REDACTED]

CCI [REDACTED]

